Post-hospital discharge measures. Patients will begin daily evening electronic diary entries on the day of hospital discharge for 60 days. These assessments will typically take less than 2 minutes and assess IMMPACT recommended domains (Turk, 2006): pain intensity, physical functioning, emotional functioning, and participant ratings of global improvement and associated symptoms. Electronic diary entries are captured wirelessly using the participant's home wireless connection via a customized, secure database. Several tablets equipped with pre-paid 4G wireless access will be available to ensure that participants without home internet connections can participate. The diaries will be monitored and maintained by research personnel in real-time; if a participant misses a diary entry, they will be emailed or called (their preference) to ensure maximal adherence to the protocol. Using these procedures we have been able to obtain > 95% adherence in our previous diary studies. Participants will also wear the accelerometer for the first 60 days after discharge. Participants will also complete the cognitive tasks (Iowa gambling task, Wisconsin card sort, TSK) that they were introduced to at the baseline session at 2 months after hospital discharge. These tasks will again be administered via the PEBL software. Questionnaires done at pre-randomization will be repeated at 2 months after surgery. We will also record objective assessments of joint function at the times when the subjects return to clinic for their postoperative visits. Finally, we will contact each participant by telephone monthly until 6 months after surgery and at one year after surgery with a brief (<10 min) series of questions regarding their pain, physical function, and disability (12 item WHODAS 2.0) following surgery.

Subject payment: Subjects will be paid \$700 with pro-rated payment steps (listed below) to study completion. The tablet devices will be returned to each study center for re-use. Pro-rated payment will be made as follows:

- \$100 for completion of the first HPRU study visit
- \$100 for completion of the second HPRU study visit
- \$100 for return of study supplies (electronic tablet, accelerometer and chargers)

- \$200 for completing at least 90% of the daily diary entries on the electronic tablet and wearing the accelerometer through 8 weeks after surgery at least 90% of required time
- \$200 for completion of all the scheduled study visits and telephone questionnaires

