Statistical Power Considerations. Enrolling $N = 120$ participants ($n = 60$ per study arm) provides sufficient power to examine the study's primary hypothesis. Assuming that each individual contributes ~ 60 daily measurements, with $\alpha = 0.05$, $\text{power} = .80$, a modest level of within-subject correlation, and adequate model fits (SD of the residuals < 2.0), we will be able to detect difference in slopes of $d = 0.09$ units. Thus, if the saline group exhibited a mean pain score of 8.0 VAS units after surgery and decreased on average 0.38 points each day (i.e., expected full recovery at 21 days), sufficient power exists to detect an enhanced slope of 0.47 in

the oxytocin group (i.e., expected full recovery in ~17 days). This difference is a clinically meaningful effect size that could substantially improve the life of patients.

Outcome measures.

Primary outcome measure: Modeled trajectory of recovery from pain (worst daily pain intensity) using a log of time form.

Several secondary analyses are planned, including slope of modeled change in other pain intensity measures (daily average pain and pain right now), activity and cognitive function tests. Interaction between preoperative cognitive style and slope of modeled change in these measures. that examine changes in cognition (e.g., impulsivity, attention) as well as kinesiphobia. The cognition measures (Iowa gambling task, Wisconsin card sort, TSK) collected at baseline and 2 months after discharge will be examined using generalized linear model with time as a fixed factor.

Human subjects protection.

Subject recruitment methods. Appropriate subjects will be identified and approached in the Department of Orthopedics during their regular scheduled appointment, by research personnel. Research personnel will utilize a private exam room to talk with subjects. Subjects will be given the study details and the opportunity to read the informed consent. The subject may take the informed consent home and make their decision regarding study participation. Contact information for the research staff will be provided to the subject so that they may call for questions or to participate. Study personnel will make every effort to approach any subject that will be scheduled for primary HA.

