Study objective: The primary objective is to determine the effectiveness of intrathecal oxytocin to speed recovery from pain, as measured by growth curve modeling, after TKA.

Secondary objectives are:

- a. To determine the effectiveness of oxytocin to speed gain in activity, assessed by actigraphy and analyzed by growth curve modeling, after TKA
- b. To determine the effectiveness of oxytocin to speed recovery from self-assessed disability, as measured by growth curve modeling, after TKA
- c. To determine the effectiveness of oxytocin to hasten time to cessation of opioid use, as measured by growth curve modeling, after TKA

Section 3: Trial Methods

9. *Trial design*

The trial is a single center, randomized, parallel-group, placebo-controlled trial. Treatment allocation is a 1:1 ratio. Patients are randomized to either oxytocin or saline control.

10. *Randomization*

Participants were randomized into treatment arms in a 1:1 ratio using permuted blocks of sizes 4 to 8. Randomization assignments. The ‘blockrand’ package in R was used by the study statistician. Allocation concealment was maintained using a centralized pharmacy administration of study drug. Both study agents are designed to look identical to each other to maintain blinding.

11. *Sample size*

Enrolling $N = 120$ participants ($n = 60$ per study arm) provides sufficient power to examine the study’s primary hypothesis. Assuming that each individual contributes ~ 60 daily measurements, with $\alpha = 0.05$, power = .80, a modest level of within-subject correlation, and adequate model fits (SD of the residuals < 2.0), we will be able to detect difference in slopes of $d = 0.09$ units. Thus, if the saline group exhibited a mean pain score of 8.0 VAS units after surgery and decreased on average 0.38 points each day (i.e., expected full recovery at 21 days), sufficient power exists to detect an enhanced slope of 0.47 in the oxytocin group (i.e., expected full recovery in ~ 17 days). This difference is a clinically meaningful effect size that could substantially improve the life of patients.

12. *Framework*

Superiority testing will be used to examine differences between the treatment arms.

13a. *Information on interim analyses*

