There were no planned interim analyses. An interim analysis was performed on Feb 8, 2019 after 49 subjects had completed the 2 month daily diary portion of the study. This was performed by the study statistician for the purpose of an NIH grant submission, with the study team remaining blinded to allocation assignments. Only descriptive statistics were performed and there was a decision prior to the analysis that early stopping would not be allowed based on the results.

13b. *Any planned adjustment of the significance level due to interim analysis*

None.

13c. *Details of guidelines for stopping a trial early*

There was no plan to stop the trial early aside from recommendations based on unanticipated serious adverse events by the DSMB.

14. *Timing of final analysis*

Final analysis of the oxytocin vs saline comparison will take place when all patients have completed the 12 month follow-up and data for the primary endpoint have been cleaned (anticipated January 2022). The first main report/publication of the primary endpoint will be prepared for submission, anticipated by May, 2022.

15. *Timing of outcome assessments*

The schedule of study procedures is provided in the protocol and summarized in the table below.

Phase	Ortho Clinic	V1 (COMPLETED 2-4 WEEKS PRIOR TO SURGERY)	14 DAYS Pre op- 1 day pre op	DOS	POD 1	POD 2- POD 56	Post op Week 1-8	Post op V2 (8-10 weeks)	Monthly follow up 3 mos	Monthly follow up 4 mos	Monthly follow up 5 mos	Monthly follow up 6 mos	Monthly follow up 12 mos
Obtain/Confirm Informed Consent	X	X		X									
Obtain Medical History	X	X											
Urine Pregnancy Test if applicable				X									
Questionnaires		X						X					
Iowa Gambling		X						X					
Card Sorting		X						X					
Daily Diary			X	X	X	X							
Weekly Diary (WHODAS)							X						
Step tracker			X		X	X							
Verbal Pain				X	X								
Monthly Diary									X	X	X	X	X

Section 4: Statistical Principles

16. *Level of statistical significance*

All applicable statistical tests will be 2-sided and will be performed using a 5% significance level.

17. *Adjusting for multiplicity*

The primary analysis involves a single model-based inference that will be interpreted at the 5% threshold of statistical significance. Multiple secondary outcomes will be evaluated and each will be interpreted at the 5% level of significance with no adjustments made for multiplicity.

18. *Confidence intervals*

All confidence intervals presented will be 95% and two-sided.

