The level of consent withdrawal will be tabulated (classified as “consent to continue follow-up and data collection” “consent to continue data collection only”, “complete – no further follow-up or data collection”).

24b. *Timing of withdrawal/lost to follow up data*

This will be presented in CONSORT diagram format rather than as a table, with numbers and reasons for withdrawal and/or exclusion from analysis given at each stage

24c. *Reasons for withdrawal/lost to follow up data*

The numbers (with reasons, if available) of losses to follow-up (drop-outs and withdrawals) over the course of the trial will be summarized by treatment arm.

25a. *List of baseline characteristics to be summarized*

Patients will be described with respect to age, sex, race, ethnicity, medications, number of painful conditions excepting the hip and their locations, questionnaire and cognitive game scores, baseline pain and activity from the daily diaries prior to surgery, attending surgeon, and surgical approach (anterior vs posterior).

25b. How baseline characteristics will be described

Categorical data will be summarized by numbers and percentages. Continuous data will be summarized by mean, SD and range if data are normal and median, IQR and range if data are skewed. Minimum and maximum values will also be presented for continuous data. Tests of statistical significance will not be undertaken for baseline characteristics; rather the clinical importance of any imbalance will be noted.

Section 5: Analysis

26. Outcomes and timings

Primary outcome: Worst pain intensity measured using a 0 to 10 numerical rating scale on a daily diary. Measurements will be obtained each evening from day 0 (surgery) to day 56 after surgery. The pain measurements will be evaluated in a statistical model using an intercept (i.e., immediate pain after surgery) and slope (i.e., rate of change of pain during the observation period).

Secondary outcomes: Daily measurements such as physical activity, as measured via actigraphy, disability, as measured by daily diaries and weekly WHODAS 2.0 scores, and opioid self-administration, as measured by daily diaries will be collected from day 0 (surgery) to day 56 after surgery.

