These individual predictors sets will then be used to test the primary hypothesis that oxytocin alters time course of recovery after TKA. The primary statistical inference will be a likelihood ratio comparing two models estimated with and without oxytocin group assignment. Thus, the pain trajectory model comparing medication assignment (oxytocin versus placebo) adjusted for the covariates of characteristics and preoperative study data will be compared to a similar model without medication assignment using a Chi-squared test. This approach allows a single direct test of the primary hypothesis and will be interpreted using a two-tailed hypothesis test using $p < 0.05$. A statistically significant difference will be interpreted as evidence to support the primary hypothesis that pain trajectory differs between oxytocin and saline treatment.

Secondary analyses: Trajectories for daily activity, as measured via actigraphy, disability, as measured by daily diaries and weekly WHODAS 2.0 scores, and opioid self-administration, as measured by daily diaries, will be analyzed using a similar approach to that of the primary outcome, with one exception. For the activity analysis, preoperative data covariate included will not be pain, but rather degree of daily actigraphy activity and its variance during the two weeks prior to surgery as assessed by daily diaries. For disability analysis, preoperative data covariate included will not be pain, but rather degree of daily disability and its variance during the two weeks prior to surgery as assessed by daily diaries and baseline WHODAS 2.0 score. As noted, with the exception of the PROMIS depression score, other questionnaire and cognitive game scores will be described for the two groups but not analyzed or entered as covariates for the purpose of the primary analysis and publication. Changes in questionnaire data will be evaluated using the generalized linear model regressing follow-up score on baseline score and medication group assignment.

27c. Methods to be used for assumptions to be checked for statistical methods for primary and secondary analyses

The assumptions underlying parametric modeling will be evaluated using regression diagnostic procedures and histograms of residuals.

27d. Alternative methods to be used if distributional assumptions do not hold for primary and secondary analyses

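### The SAP omits, without explanation, the protocol's secondary slopes for daily average pain and pain right now, while listing disability and opioid use, which the protocol's secondary list does not name

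*Protocol*

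**What the plan says.** **Protocol, Outcome measures.** The primary outcome is the modelled trajectory of worst daily pain in log time. The secondary list opens with "Several secondary analyses are planned, including" and its first entry is the "slope of modeled change in other pain intensity measures (daily average pain and pain right now". Activity, cognitive function tests and an interaction with preoperative cognitive style follow. Disability and opioid use are not on the list.

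**Protocol, Table 1 and Post-hospital discharge measures.** Disability is collected all the same. WHODAS 2.0 is among the preoperative questionnaires, which are repeated at 2 months, and the telephone contacts ask "regarding their pain, physical function, and disability (12 item WHODAS 2.0) following surgery".

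**SAP items 8 and 26.** Item 26 keeps the primary outcome: "Primary outcome: Worst pain intensity measured using a 0 to 10 numerical rating scale on a daily diary". Its secondary outcomes are "Daily measurements such as physical activity, as measured via actigraphy, disability" and opioid self-administration. Item 8 sets matching objectives, for example "To determine the effectiveness of oxytocin to speed recovery from self-assessed disability, as measured by growth curve modeling, after TKA", and one on stopping opioids.

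**SAP item 27.** These secondary trajectories are modelled much as the primary is. Other questionnaire scores and the cognitive game scores "will be described for the two groups but not analyzed or entered as covariates", a restriction that the same sentence confines to the primary analysis and its publication.

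**SAP items 3, 4 and 17.** The SAP is based on protocol version 1.0 of December 13, 2016. The revision log has one entry, dated Dec 15, 2021, for details supplied when data acquisition was over and unblinding had not occurred. For the secondary outcomes, "each will be interpreted at the 5% level of significance with no adjustments made for multiplicity".

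**The concern.** Worst, average and current pain are three ratings of one construct, and the protocol meant all three to be analysed by slope. The two secondary slopes are the most direct check on whether a result for worst pain, positive or null, holds for pain in general. An analyst who follows the SAP will not fit them and a reader of the report will not see them, although the governing protocol promised both.

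Disability and opioid use appear beside activity as full secondary objectives, with no note that the protocol's list did not name them. Without a dated reason for either change, a reader has no record from which to judge whether these outcomes were chosen independently of the data.

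**Working it through.** **1. The plan's own figures.** The only numerical planning statement concerns the primary outcome: 8.0/0.38 = 21.1 days, 8.0/0.47 = 17.0 days, and 0.47 − 0.38 = 0.09. These agree with the stated 21 days, about 17 days and 0.09. No figure is given for any secondary outcome, so the check is a comparison of the two lists.

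**2. The lists side by side.**

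| Measure | Protocol, Outcome measures | SAP items 8, 26, 27 |
|---|---|---|
| Worst daily pain, log time | Primary | Primary |
| Daily average pain, slope | Secondary | Absent |
| Pain right now, slope | Secondary | Absent |
| Activity | Secondary | Secondary trajectory |
| Iowa gambling, card sorting | Secondary | Described only, for the primary publication |
| TSK | Secondary (also a Table 1 questionnaire) | Unclear: item 27 also plans a regression of follow-up on baseline questionnaire scores and treatment group |
| Disability | Not named (WHODAS 2.0 collected) | Secondary trajectory, daily diary and weekly WHODAS |
| Opioid use after discharge | Not named | Secondary: time to cessation in item 8, self-administration trajectory in items 26 and 27 |

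**3. Count.** The protocol plans two pain slopes besides the primary, and the SAP has none of them. The SAP has three secondary trajectory domains. The protocol's list names one (activity) and does not name two (disability, opioid use).

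**4. Is a reason recorded?** No. Item 3 cites no protocol amendment. The log in item 4 refers only to a Section 6 and lists no outcome. The SAP's headed sections stop at Section 5. Because Section 4 is used twice, the Analysis section is sixth in order and may be what is meant. But item 8, which names disability and opioid use, lies in Section 2, where the log records no change. If the log is complete, those two objectives were already in SAP version 1.0. That version and its date are not supplied, so the timing cannot be settled.

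**5. Can the two slopes be fitted?** The protocol plans daily diary ratings of pain intensity and names both measures as daily or current ratings to be modelled. I assume that both items were in the diary as fielded. The SAP neither confirms nor denies it, since worst pain is the only diary pain rating it specifies.

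**The case against.** The strongest reply is that little was lost and nothing was hidden. The primary outcome and its log-time form are intact, and the primary inference is one test. The log places version 2.0 before unblinding. The protocol's list is open, so additions are allowed, and disability is largely the promotion of data already planned. All of this stands and limits the point to secondary results. It does not answer the omission: an open list permits additions, but it does not explain why two named items have gone. The limit to the primary publication covers questionnaire and cognitive scores, and the SAP promises no later analysis of the two pain slopes.

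A reader might infer more than the documents support:

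- **That outcomes were switched with all data in hand.** Version 1.0 is missing and the log does not mention outcomes. What is shown is that the list is found in a SAP completed after data acquisition.
- **That the secondary evidence is therefore biased.** A choice made without sight of results by arm does not by itself bias the treatment comparison. The unplanned look in February 2019 (item 13a) was run by the study statistician on 49 subjects, was descriptive, and left the study team blinded. Whether it was by arm is not stated, so it proves nothing either way.
- **That two families are missing and only activity is still analysed.** The two pain slopes are one family. The cognitive scores are still described, and TSK may fall under the questionnaire regression.
- **That unadjusted testing makes the case.** Three independent tests at 5% give 1 − 0.95³ = 14.3%. Activity with the two restored slopes is also three tests and gives the same figure. Unadjusted testing is openly declared in item 17, and the protocol likewise set p < 0.05 with no adjustment described.

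**Conclusion.** The point holds as a mismatch between the two documents. Two secondary pain slopes named in the protocol are absent from the SAP with no reason given, and two outcome domains that the protocol's list does not name stand as secondary objectives with no date or reason. The primary analysis and the sample size are unaffected.

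What is at stake is the completeness and traceability of the secondary results. The documents do not establish when the list changed, or that knowledge of results played any part. The conclusion rests on the two documents as supplied and would be softened, for disability and opioid use only, by a SAP version 1.0 that named them before data acquisition.

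**What to change.** 1. Add growth-curve analyses of daily average pain and pain right now to SAP items 26 and 27, with the same log-time model and covariates as worst pain, and report both whatever the result. If either item was not collected, say so.
2. In items 8 and 26, identify disability and opioid use as secondary outcomes that the protocol does not name, with the date and reason for each. Treat them as exploratory unless an earlier SAP version shows that they were specified before data acquisition. They should not be labelled as introduced in version 2.0 unless version 1.0 confirms it.
3. Enter these changes in the revision log under the correct section, stating whether unblinding has occurred.

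The cost is two further model fits on diary data that the protocol already planned, and a few lines of text. The downside is possibly less confirmatory wording for disability and opioid use.

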Appendix

1. Copies of each questionnaires or surveys that will be used
2. Consent form

Unique Protocol ID: IRB00036246

Title: Efficacy of Intrathecal Oxytocin to Speed Recovery After Hip
Surgery

NCT03011307

Document Date: 1/03/2022

Section 1: Administrative information

1.a. Title

Statistical analysis plan for Efficacy of Intrathecal Oxytocin to Speed Recovery from Hip Surgery: a single-center randomized controlled trial to assess whether a single intrathecal injection of oxytocin at the time of total hip arthroplasty (TKA) hastens recovery from pain over the next 2 months.

1.b. Trial registration

Trial Registration: NCT03011307

2. SAP version

Version: 2.0 Date: December 15, 2021

3. Protocol Version

This document has been written based on information contained in the study protocol version 1.0, dated December 13, 2016.

4. SAP Revisions

[figure not shown]
Protocol version	Updated SAP version no.	Section number changed	Description and reason for change	Date changed
1.0	2.0	Section 6	Details provided after data acquisition and before unblinding	Dec 15, 2021

5. Roles and Responsibilities – non-signatory names and contribution

[name].
Professor of Anesthesiology
Wake Forest School of Medicine
Winston-Salem, NC
Role: Chief investigator

[name].
Associate Professor of Anesthesiology
Massachusetts General Hospital
Boston, MA
Role: Co-investigator and Senior Statistician

6.a. Roles and Responsibility – signature of the person writing the SAP

01/03/2022

[name].
Chief Investigator

Date

6.b. Roles and Responsibility – signature of senior statistician responsible

01/03/2022

[name].
Co-Investigator & Senior Statistician

Date

Section 2: Introduction

7. *Background and Rationale*

Recovery from pain after surgery varies greatly among individuals, with some who are pain free within days and others who experience pain for years. Recovery from pain after cesarean delivery is more rapid than after other pelvic surgeries, and work in animals suggest this reflects actions of the hormone oxytocin in the spinal cord. This study is the first to test whether intrathecal injection of oxytocin at the time of surgery will speed recovery from pain after surgery.

8. *Objectives*

Research hypothesis: The null hypothesis is that there is no difference in modeled trajectory of change in pain intensity report after TKA between intrathecal injection of saline and of oxytocin. The alternative hypothesis is that there is a difference between the two groups.

Study objective: The primary objective is to determine the effectiveness of intrathecal oxytocin to speed recovery from pain, as measured by growth curve modeling, after TKA.

Secondary objectives are:

- a. To determine the effectiveness of oxytocin to speed gain in activity, assessed by actigraphy and analyzed by growth curve modeling, after TKA
- b. To determine the effectiveness of oxytocin to speed recovery from self-assessed disability, as measured by growth curve modeling, after TKA
- c. To determine the effectiveness of oxytocin to hasten time to cessation of opioid use, as measured by growth curve modeling, after TKA

Section 3: Trial Methods

9. *Trial design*

The trial is a single center, randomized, parallel-group, placebo-controlled trial. Treatment allocation is a 1:1 ratio. Patients are randomized to either oxytocin or saline control.

10. *Randomization*

Participants were randomized into treatment arms in a 1:1 ratio using permuted blocks of sizes 4 to 8. Randomization assignments. The ‘blockrand’ package in R was used by the study statistician. Allocation concealment was maintained using a centralized pharmacy administration of study drug. Both study agents are designed to look identical to each other to maintain blinding.

11. *Sample size*

Enrolling $N = 120$ participants ($n = 60$ per study arm) provides sufficient power to examine the study’s primary hypothesis. Assuming that each individual contributes ~ 60 daily measurements, with $\alpha = 0.05$, power = .80, a modest level of within-subject correlation, and adequate model fits (SD of the residuals < 2.0), we will be able to detect difference in slopes of $d = 0.09$ units. Thus, if the saline group exhibited a mean pain score of 8.0 VAS units after surgery and decreased on average 0.38 points each day (i.e., expected full recovery at 21 days), sufficient power exists to detect an enhanced slope of 0.47 in the oxytocin group (i.e., expected full recovery in ~ 17 days). This difference is a clinically meaningful effect size that could substantially improve the life of patients.

12. *Framework*

Superiority testing will be used to examine differences between the treatment arms.

13a. *Information on interim analyses*

There were no planned interim analyses. An interim analysis was performed on Feb 8, 2019 after 49 subjects had completed the 2 month daily diary portion of the study. This was performed by the study statistician for the purpose of an NIH grant submission, with the study team remaining blinded to allocation assignments. Only descriptive statistics were performed and there was a decision prior to the analysis that early stopping would not be allowed based on the results.

13b. *Any planned adjustment of the significance level due to interim analysis*

None.

13c. *Details of guidelines for stopping a trial early*

There was no plan to stop the trial early aside from recommendations based on unanticipated serious adverse events by the DSMB.

14. *Timing of final analysis*

Final analysis of the oxytocin vs saline comparison will take place when all patients have completed the 12 month follow-up and data for the primary endpoint have been cleaned (anticipated January 2022). The first main report/publication of the primary endpoint will be prepared for submission, anticipated by May, 2022.

15. *Timing of outcome assessments*

The schedule of study procedures is provided in the protocol and summarized in the table below.

Phase	Ortho Clinic	V1 (COMPLETED 2-4 WEEKS PRIOR TO SURGERY)	14 DAYS Pre op- 1 day pre op	DOS	POD 1	POD 2- POD 56	Post op Week 1-8	Post op V2 (8-10 weeks)	Monthly follow up 3 mos	Monthly follow up 4 mos	Monthly follow up 5 mos	Monthly follow up 6 mos	Monthly follow up 12 mos
Obtain/Confirm Informed Consent	X	X		X									
Obtain Medical History	X	X											
Urine Pregnancy Test if applicable				X									
Questionnaires		X						X					
Iowa Gambling		X						X					
Card Sorting		X						X					
Daily Diary			X	X	X	X							
Weekly Diary (WHODAS)							X						
Step tracker			X		X	X							
Verbal Pain				X	X								
Monthly Diary									X	X	X	X	X

Section 4: Statistical Principles

16. *Level of statistical significance*

All applicable statistical tests will be 2-sided and will be performed using a 5% significance level.

17. *Adjusting for multiplicity*

The primary analysis involves a single model-based inference that will be interpreted at the 5% threshold of statistical significance. Multiple secondary outcomes will be evaluated and each will be interpreted at the 5% level of significance with no adjustments made for multiplicity.

18. *Confidence intervals*

All confidence intervals presented will be 95% and two-sided.

19a. *Definition of adherence to the intervention and how it is assessed*

Compliance is assessed based on the number of daily diary entries after hospital discharge. It is defined as:

$\% \text{ compliance} = (\text{number of entries} / \text{number of days entries were to be completed}) * 100\%$

19b. *How adherence will be presented*

The number and % of participants completing more than 80% of the daily diaries after surgery will be provided by treatment group in a table. All available data will be included in the analysis from the intention to treat sample.

19c. *Definition of protocol deviation*

The following are pre-defined major protocol violations with a direct bearing on the primary outcome:

1) Surgery during the primary outcome assessment period (first 8 weeks after TKA surgery)

19d. *Description of which protocol deviations will be summarized*

Protocol deviations are classified prior to unblinding of treatment. The number (and percentage) of patients with major and minor protocol deviations will be summarized by treatment group with details of type of deviation provided. The patients that are included in the ITT analysis data set will be used as the denominator to calculate the percentages. No formal statistical testing will be undertaken.

20. *Analysis population*

The intention-to-treat population will include all randomized patients who received study drug.

Section 4. Trial Population

21. *Screening data*

Enrollment: The dates of recruitment, the number of patients screened, the number of patients recruited, the number of screened patients not recruited, and the reason for non-recruitment will be reported as part of the CONSORT diagram.

22. *Eligibility criteria*

Inclusion and exclusion criteria are provided in the protocol. The number of ineligible patients randomized, if any, will be reported, with reasons for ineligibility

23. *Information to be reported in the CONSORT flow diagram*

A CONSORT flow diagram (appendix A) will be used to summarize the number of patients who were:

- assessed for eligibility at screening
- eligible at screening
- ineligible at screening*
- eligible and randomized
- eligible but not randomized*
- received the randomized allocation
- did not receive the randomized allocation*
- lost to follow-up*
- discontinued the intervention*
- randomized and included in the primary analysis

*reasons will be provided for post randomization exclusions.

24a. *Description of level of withdrawal*

The level of consent withdrawal will be tabulated (classified as “consent to continue follow-up and data collection” “consent to continue data collection only”, “complete – no further follow-up or data collection”).

24b. *Timing of withdrawal/lost to follow up data*

This will be presented in CONSORT diagram format rather than as a table, with numbers and reasons for withdrawal and/or exclusion from analysis given at each stage

24c. *Reasons for withdrawal/lost to follow up data*

The numbers (with reasons, if available) of losses to follow-up (drop-outs and withdrawals) over the course of the trial will be summarized by treatment arm.

25a. *List of baseline characteristics to be summarized*

Patients will be described with respect to age, sex, race, ethnicity, medications, number of painful conditions excepting the hip and their locations, questionnaire and cognitive game scores, baseline pain and activity from the daily diaries prior to surgery, attending surgeon, and surgical approach (anterior vs posterior).

25b. How baseline characteristics will be described

Categorical data will be summarized by numbers and percentages. Continuous data will be summarized by mean, SD and range if data are normal and median, IQR and range if data are skewed. Minimum and maximum values will also be presented for continuous data. Tests of statistical significance will not be undertaken for baseline characteristics; rather the clinical importance of any imbalance will be noted.

Section 5: Analysis

26. Outcomes and timings

Primary outcome: Worst pain intensity measured using a 0 to 10 numerical rating scale on a daily diary. Measurements will be obtained each evening from day 0 (surgery) to day 56 after surgery. The pain measurements will be evaluated in a statistical model using an intercept (i.e., immediate pain after surgery) and slope (i.e., rate of change of pain during the observation period).

Secondary outcomes: Daily measurements such as physical activity, as measured via actigraphy, disability, as measured by daily diaries and weekly WHODAS 2.0 scores, and opioid self-administration, as measured by daily diaries will be collected from day 0 (surgery) to day 56 after surgery.

Questionnaire and cognitive game data will be assessed at baseline and follow-up. Validated scoring systems from the individual items will be used to score each questionnaire or measure. For the purpose of the primary analysis publication, summary scores with measure of central tendency and variance will be provided for oxytocin and saline groups as mentioned in Item 25b.

27a. Analysis methods to be used and

27b. Adjustments for covariates

Primary analysis:

To examine how participants recover over the repeated measurement occasions, we will employ hierarchical linear modeling (HLM) [1]. The application of HLM to individual change data is well suited for the expected changes that occur after surgical injury. HLM is a polynomial regression with random effects where interaction terms are used to examine impacts on the change parameters (e.g., treatment group x intercept; treatment group x slope). Because of the nature of the expected change, the trajectories will be modeled using parameters consisting of an intercept and the slope estimated using the natural log of time (change in recovery). The intercept is coded to represent the initial level (first day after hospital discharge) of the outcome variable. The slope estimates the change over ln of time and represents the increase or decrease in the variable. Through the use of fixed and random effects, we will then be able to examine the influences on the changes in pain. In this way, we test efficacy of the test intervention, intrathecal oxytocin.

To examine the proposed hypothesis, we have *a priori* defined key fixed effects that will be included in the primary model, based on previous literature regarding their influence on recovery after surgery. This adjusted analysis is the primary analysis. Each of these predictors is described below:

Oxytocin: Randomized treatment assignment of either oxytocin or placebo will be a fundamental predictor of trajectory.

Patient characteristics: To adjust the associations for individual characteristics, age, sex, number of painful conditions beyond the operated hip, ongoing use of opioids at the time of recruitment, and PROMIS depression score will be entered into the model.

Preoperative study data: Degree of daily pain and its variance during the two weeks prior to surgery as assessed by daily diaries will be entered into the model.

These individual predictors sets will then be used to test the primary hypothesis that oxytocin alters time course of recovery after TKA. The primary statistical inference will be a likelihood ratio comparing two models estimated with and without oxytocin group assignment. Thus, the pain trajectory model comparing medication assignment (oxytocin versus placebo) adjusted for the covariates of characteristics and preoperative study data will be compared to a similar model without medication assignment using a Chi-squared test. This approach allows a single direct test of the primary hypothesis and will be interpreted using a two-tailed hypothesis test using $p < 0.05$. A statistically significant difference will be interpreted as evidence to support the primary hypothesis that pain trajectory differs between oxytocin and saline treatment.

Secondary analyses: Trajectories for daily activity, as measured via actigraphy, disability, as measured by daily diaries and weekly WHODAS 2.0 scores, and opioid self-administration, as measured by daily diaries, will be analyzed using a similar approach to that of the primary outcome, with one exception. For the activity analysis, preoperative data covariate included will not be pain, but rather degree of daily actigraphy activity and its variance during the two weeks prior to surgery as assessed by daily diaries. For disability analysis, preoperative data covariate included will not be pain, but rather degree of daily disability and its variance during the two weeks prior to surgery as assessed by daily diaries and baseline WHODAS 2.0 score. As noted, with the exception of the PROMIS depression score, other questionnaire and cognitive game scores will be described for the two groups but not analyzed or entered as covariates for the purpose of the primary analysis and publication. Changes in questionnaire data will be evaluated using the generalized linear model regressing follow-up score on baseline score and medication group assignment.

27c. Methods to be used for assumptions to be checked for statistical methods for primary and secondary analyses

The assumptions underlying parametric modeling will be evaluated using regression diagnostic procedures and histograms of residuals.

27d. Alternative methods to be used if distributional assumptions do not hold for primary and secondary analyses

